### 2.3 Project design

We will conduct a single-center, prospective, observational study at the General Hospital Solothurn. The study will be conducted at the Department of Emergency Medicine, where patients will be screened for hyponatremia, and the Department of General Internal Medicine, where screening will occur both in the inpatient and outpatient services.

### 3 PROJECT POPULATION AND STUDY PROCEDURES

#### 3.1 Project population, inclusion and exclusion criteria

Sample size was calculated on basis of the MOCA test. To achieve a power of 90% and a two-sided alpha level of 0.05, the sample size needed to detect a difference of 5 points (shown difference between normal individuals and those with mild cognitive impairment) between the baseline and post-correction MOCA scores would be 44 patients [23]. Thus, we plan to enroll a total of 50 patients.

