### 2.2 Primary and secondary endpoints

- A) Muscle strength in pounds and kilogram before and after correction of hyponatremia.
- B) Results for the Tinetti performance-oriented mobility assessment (POMA) to evaluate static and dynamic balance abilities during and after correction of hyponatremia.
- C) Results for the Montreal Cognitive Assessment (MOCA) test to assess mild cognitive impairment before and after correction of hyponatremia.

Muscle strength at handgrip will be measured at time of presentation at our clinic with a serum sodium  $\leq 125$  mmol/L and 24 to 48 hours after correction of hyponatremia at a serum sodium  $\geq 135$  mmol/L using the Jamar® hydraulic hand dynamometer, Lafayette Instrument, Lafayette, IN, USA. Strength will be measured in pounds and kilograms thrice at baseline and after correction of hyponatremia, respectively. The best result of each test will be used for the analysis. The test will be conducted by either Drs. [name] or [name].

The Tinetti POMA, a simple, easily administered test, will be used to measure patients' gait and balance taking about 10 to 15 minutes [19]. Scoring of the Tinetti Assessment Tool is done on a three point ordinal scale with a range of 0 to 2. A score of 0 represents the most severe impairment, while a 2 would represent patient independence. The individual scores are then combined to form three measures; an overall gait assessment score, an overall balance assessment score, and a gait and balance score. The test has been validated in several studies and found to be a useful screening tool for gait instabilities and prediction of falls [20-22]. The Tinetti POMA form is shown in the Appendix. The test will be performed at baseline and 24 to 48 hours after correction of hyponatremia. The test will be conducted by either Drs. [name] and [name].

The MOCA is a 30-point test administered in about 10 minutes designed to identify mild cognitive impairment [23]. The test is validated for a large variety of diseases ranging from frontotemporal dementia to HIV or chronic obstructive pulmonary disease [24-27]. The MOCA form is shown in the Appendix. The test will be performed at baseline and 24 to 48 hours after correction of hyponatremia. The test will be conducted by either Drs. [name] and [name].

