### 3.4 Withdrawal and discontinuation

Patients are excluded from the project in case of withdrawal of informed consent. Endpoint-specific datasets will be included if complete (see Section 4.2.). Additional patients will be enrolled to compensate for drop-outs. Since the blood samples used are part of clinical routine no further steps are taken, the blood samples will be handled according to usual clinical routine.

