## 4 STATISTICS AND METHODOLOGY

### 4.1. Statistical analysis plan

Data will be presented as means and standard deviation or medians and interquartile range as appropriate. Wilcoxon signed ranked tests will be used to compare results on muscle strength, Tinetti score and MOCA scores, since those are not normally distributed and samples will be dependent since every patient serves as his own control. A p-value of  $\leq 0.05$  will be considered statistically significant. Statistics will be calculated using IBM SPSS Statistics 25, IBM, Armonk, New York, USA.

Based on general Patient count and prevalence of Hyponatremia, the enrollment of the sample size of 50 patients seems realistic in a 12-month period, starting on 01 June 2019.

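### Does the missing SD of the MOCA change make the 44-patient sample size unsound?

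*Protocol*

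**What the plan says.** Section 3.1 of the Protocol sizes the study on the MOCA. With 90% power and "a two-sided alpha level of 0.05" it reports "the sample size needed to detect a difference of 5 points (shown difference between normal individuals and those with mild cognitive impairment" as the target, and the figure "between the baseline and post-correction MOCA scores would be 44 patients [23" follows with a citation to reference 23. The next sentence reads "Thus, we plan to enroll a total of 50 patients".

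Section 4.1 fixes the comparison as paired, because "samples will be dependent since every patient serves as his own control", and names the test: "Wilcoxon signed ranked tests will be used to compare results on muscle strength, Tinetti score and MOCA scores". Section 2.2 gives the scale: "The MOCA is a 30-point test administered in about 10 minutes". Section 3.4 deals with losses: "Additional patients will be enrolled to compensate for drop-outs".

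The Protocol gives no SD of the paired change, no SD at a single visit, no correlation between visits and no name for the sample size method.

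**The concern.** In a paired design the number of patients depends on the target difference divided by the SD of the within-patient change. Section 3.1 gives the numerator only, so 44 cannot be reproduced from the stated inputs.

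Two features make the gap look like more than an omission. First, the SD that 44 implies is about 10 points on a 30-point test, which seems large for the same person tested twice. Second, the Protocol itself describes the 5 points as separating normal from mildly impaired people, which is a contrast between persons, yet applies it to a before-and-after difference. Together these raise the suspicion that a calculation for two independent groups was used for a paired study.

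At stake would be the stated sensitivity. If the SD were much smaller than 10, the study could detect changes well below 5 points, and a reader might misjudge a null result or a small significant change. If it were larger, power would be below 90%.

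**Working it through.** **Inputs.** From section 3.1: difference 5 points, power 90%, two-sided alpha 0.05, n = 44, enrolment 50. From section 4.1: paired design, Wilcoxon signed-rank test. From section 2.2: 30-point scale. The SD of change is not given, so it is solved for and then varied.

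**1. The plan's figure, solved backwards.**

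- Normal approximation: SD = 5 × √44 / (1.960 + 1.282) = 33.17 / 3.242 = 10.2.
- Paired t-test (noncentral t): 90% power at n = 44 needs a standardised effect of 0.500, so SD = 5 / 0.500 = 10.0. With SD 10, power is 0.9000 at n = 44 and 0.893 at n = 43, so 44 is exactly the smallest adequate number.
- Wilcoxon signed-rank (simulation, normal untied differences): at a standardised effect of 0.5, power is 0.887 with 44 pairs, 0.900 with 46, 0.905 with 47 and 0.923 with 50. With 44 pairs, 90% power needs an effect of about 0.511, so SD = 5 / 0.511 = 9.8. Rounding the changes to whole points, which creates ties, gave 0.909 at SD 9.8 and 0.889 at SD 10.0, so ties matter little.

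**2. Is an SD of change of 10 possible on this scale?** With equal SDs at both visits, the per-visit SD is 10 / √(2(1 − r)): 7.1 at r = 0, 8.5 at r = 0.3, 10.0 at r = 0.5. Whole-number scores spread evenly over 0 to 30 have SD √((31² − 1)/12) = 8.9. The largest SD any 0-to-30 score can have is 15, so r cannot exceed 1 − 100/(2 × 225) = 0.78. An SD of 10 is therefore wide but not excluded.

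**3. Another route to 44.** For two independent groups with SD 5, n per group = 2 × (5 × 3.242 / 5)² = 21.0, rounded up to 22 by the routine used, or 44 in all. By t-test, 22 per group gives 0.8997, just short of 90%. If that were the origin, the SD of change would be 5 × √(2(1 − r)), at most 7.1 for any r of 0 or more, and paired power for 5 points would be above 99%. Nothing in the Protocol shows which route was taken.

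**4. Consequence over assumed SDs of change.** Detectable change is at 90% power, Wilcoxon, as 0.511 × SD.

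| SD of change (assumed) | Pairs needed for 5 points, paired t (Wilcoxon) | Power with 44 pairs, paired t | Detectable change, 44 pairs |
|---|---|---|---|
| 4 | 9 (10) | >99.9% | 2.0 |
| 5 | 13 (14) | >99.9% | 2.6 |
| 6 | 18 (19) | >99.9% | 3.1 |
| 8 | 29 (31) | 98.2% | 4.1 |
| 10 | 44 (47) | 90.0% | 5.1 |
| 12 | 63 (66) | 77.1% | 6.1 |

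With all 50 planned patients, Wilcoxon power for 5 points is 98.8% at SD 8 and 92.3% at SD 10. The margin between 44 and 50 allows 1 − 44/50 = 12% loss, and section 3.4 also replaces drop-outs.

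**The case for a change.** The best argument for a change is that section 3.1 is the Protocol's only statement of sensitivity and that enrolment is derived from it. The Protocol chose to report a calculation, so the omission cannot be passed to a later document. Both possible origins of 44 point the same way, towards more power than claimed, and a sentence giving the SD, its source and the method would cost nothing.

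Part of this stands. The figure cannot be reproduced from the text, and carrying a difference between persons over to a change within persons deserves a reason. Reporting the SD and method in the publication would be good practice.

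The rest does not carry. The claim that sensitivity is understated rests on assumed SDs: if some patients recover cognitively and others do not, changes could be widely spread, and beyond an SD of about 10 the direction reverses. Reference 23 is cited at exactly this sentence and is not at hand, so it cannot be said that the authors had no basis. Section 3.1 calls the 5 points a difference to detect. It does not predict that change, and a gap of clinically recognisable size is a permissible target that fits the aim of asking whether impairment reverses. Nor does powering for 5 points say that smaller changes go undetected. The study's results will be read from the observed changes and their spread, whatever SD was used in planning.

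One caution applies to both sides: ample power for 5 points is not ample power for the true effect. For a true 2-point change with 44 pairs, paired t power is 74% at SD 5 and 25% at SD 10. Writing down a planning SD would not alter that.

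**Conclusion.** The gap is real but is one of reporting. No stated figure is shown to be false: 44 is the correct paired t-test number for a standardised effect of 0.5, which for 5 points means an SD of change of 10. The planned Wilcoxon test needs about 46 to 47 pairs at that effect, and the 50 planned patients cover it with 92.3% power. For any SD below about 9.8, power for 5 points with 44 pairs exceeds 90%. At an SD of 12 it would be 77% by paired t.

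Followed as written, with 50 patients, replacement of drop-outs and a paired Wilcoxon test, the analysis of the MOCA remains sound. Stating the SD would improve transparency but leave enrolment, test and conclusions as they are, so no change to the plan follows. This rests on two points: the SDs above 10 that would leave the study short are not indicated anywhere in the Protocol, and the Wilcoxon figures assume roughly normal paired differences.

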##### *Inclusion criteria*

Consecutive patients aged 18 years or above presenting with moderately to severe hyponatremia (serum sodium  $\leq$  125 mmol/L after correction for blood glucose), who give informed consent.

##### *Exclusion criteria*

- Patients who do not give or are not able to give informed consent.
- Patients with concomitant Potassium dysregulation ( $K+ < 3.5$  mmol/l or  $K+ > 5.0$  mmol/l)
- Pregnant or Lactating females

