##### a.) Clinical data

Of all patients included in the study, we will collect data on age, sex, comorbidities, and current medications taken by the patients.

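### Acute states other than potassium disorder are neither excluded nor specifically recorded, so recovery from them between the two visits is credited to sodium correction

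*Protocol*

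**What the plan says.** Protocol section 3.1 admits "Consecutive patients aged 18 years or above presenting with moderately to severe hyponatremia", subject to consent. It lists three exclusions: "Patients who do not give or are not able to give informed consent"; "Patients with concomitant Potassium dysregulation", defined as potassium below 3.5 or above 5.0 mmol/l; and "Pregnant or Lactating females". Only the potassium criterion concerns another possible cause of the deficits under study.

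On setting and design, section 2.3 states "We will conduct a single-center, prospective, observational study at the General Hospital Solothurn" and "The study will be conducted at the Department of Emergency Medicine, where patients will be screened for hyponatremia". Inpatients and outpatients of general internal medicine are screened as well. No comparison group is described.

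On data, section 3.3 a.) states "we will collect data on age, sex, comorbidities, and current medications taken by the patients". Appendix 1 adds lines for medical history and participant characteristics at the first visit only. Neither place names acute conditions at presentation.

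On analysis, section 4.1 plans Wilcoxon signed-rank tests for grip strength, Tinetti score and MOCA on the ground that "every patient serves as his own control". No adjustment is stated. Under section 2.2 the second measurement falls 24 to 48 hours after sodium has been corrected. Section 2.1 hypothesises that correcting sodium will improve all three measures, and aim C asks whether cognitive impairment is reversible on correction.

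**The concern.** Pairing a patient with himself removes what is stable between the visits, such as age, education, chronic disease or long-standing weakness. It does not remove a state that is present at visit 1 and has eased by visit 2. A patient who is mildly intoxicated, in early withdrawal, infected, recently injured or affected by a sedating drug may test poorly on arrival and better after some days in hospital, whatever the sodium does. The planned test cannot tell that gain from a sodium effect.

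The hypothesis predicts improvement, so recovery of this kind pushes the result towards a positive finding. The word association in section 2.1 does not remove the difficulty, because aim C and the hypothesis both concern the effect of correction. What is at stake is whether a significant paired gain can be read as the protocol intends to read it.

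**Working it through.** **1. The protocol's only figure on MOCA change.** Section 3.1 gives 44 patients (50 planned) for a 5-point difference, 90% power and two-sided alpha 0.05. It states no SD, so 44 cannot be rebuilt from its own inputs. Solving the paired formula n = ((1.960 + 1.282) × SD / 5)² for n = 44 gives SD = 5 × √44 / 3.242 = 10.2. A two-group formula with SD 5 also gives 44 in total: 2 × (3.242 × 5 / 5)² = 21.0, rounded up to 22 per group. The SD of change is therefore unknown, and I use 3 to 10.

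**2. Model for unrecorded recovery.** Assume no sodium effect at all and 50 pairs. Each MOCA change is normal with mean 0 and the given SD. A random share f of patients gains a further g points from a resolving acute state. Changes are rounded to whole points and tested by a two-sided signed-rank test with zeros dropped. The documents give no value for f, g or SD; all three are assumptions.

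**3. Mean shift, f × g.**
- 0.05 × 6 = 0.3 points
- 0.10 × 4 = 0.4 points
- 0.10 × 6 = 0.6 points
- 0.20 × 6 = 1.2 points

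**4. Share of trials with p ≤ 0.05 when sodium has no effect.**

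| Affected, gain | SD 3 | SD 4 | SD 6 | SD 10 |
|---|---|---|---|---|
| none | about 5% | about 5% | about 5% | about 5% |
| 5%, 4 to 6 points | 5–8% at every SD | | | |
| 10%, 4 points | 11% | 10% | 7% | 5% |
| 10%, 6 points | 17% | 13% | 9% | 7% |
| 20%, 6 points | 49% | 38% | 24% | 13% |

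Runs differ by one to two percentage points, so I round the 10% rows at SD 3 to 4 to about 10% to 18%. A repeat with 10,000 trials per cell agreed within about 1.5 points. In the rows with 20% affected, practically every rejection was in the direction of improvement.

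**5. What the table shows.** The inflation needs a fair share of affected patients and a small SD of change. With 5% affected, or at SD 10 with 10% affected, it is slight. The shifts in step 3 are also well below the 5-point target, so these shares alone could not produce a mean gain near 5 points. The exposure is to a small gain that reaches significance. Grip and Tinetti are open to the same mechanism but are not quantified here.

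**The case against.** **The consent rule already screens.** Patients unable to consent are excluded, which will remove many who are plainly intoxicated, in severe withdrawal or badly affected by stroke. This stands and limits the share affected. It does not reach milder states, and it does nothing for gait or grip: someone with an injured limb can consent and still score low.

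**The information may be available anyway.** A reader might infer that these states go unrecorded and can never be separated later. The documents do not support that. Medical history is taken at visit 1, section 7.3 lets the investigators re-identify patients, and section 5.6 anonymises data only once analysis has ended. What is missing is a defined item, collected the same way for everyone before the results are known.

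**Such patients should then be excluded.** This is also tempting, but section 1 says hyponatremia may itself lead to falls and fractures. Excluding head or limb injury could remove the very patients whose deficit is under study, and would narrow a consecutive cohort. Where an injury prevents a test, section 4.2 already leaves out that endpoint alone and reports the reason.

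**Recovery need not be quick or one-way.** A stroke or fracture may persist, and withdrawal may begin after admission and lower the second score. The documents do not say how fast these states resolve, and the simulation allows gains only.

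**A sensitivity analysis can sit in a separate analysis plan.** True of the repeat analysis. The data item cannot wait, because data collection is fixed by the protocol and its case report form.

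**The potassium criterion may be specific to mechanism.** Section 3.1 gives no reason for it; section 1 ties sodium and potassium together through membrane potential. The point does not depend on the sponsor's motive.

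**Conclusion.** The point holds in a limited form. Potassium disorder is the only rival acute cause kept out, other acute states compatible with consent are not a specified data item, and an uncontrolled, unadjusted paired test credits their recovery to sodium correction.

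The size cannot be known from the documents. On the assumptions above, the chance of a significant MOCA gain with no sodium effect is about 10% to 18% when 10% of patients gain 4 to 6 points and the SD of change is 3 to 4. It is 7% to 9% at SD 6 and 5% to 7% at SD 10. With 20% gaining 6 points it is about 49%, 38%, 24% and 13% at SD 3, 4, 6 and 10. With 5% affected it stays at about 5% to 8%. This justifies recording the states and testing their influence. It does not show that the trial's result will be false, nor that eligibility should change.

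**What to change.** Leave the exclusions as they are.

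- **Section 3.3 a.) and Appendix 1:** add a yes/no item at visit 1 for each of acute alcohol or drug intoxication or withdrawal, new stroke or head injury, acute limb injury, acute infection, sedating drug newly started or stopped, and seizure. At visit 2, record whether each flagged condition is still present.
- **Section 4.1:** keep the analysis of all patients and pre-specify a repeat of the three Wilcoxon tests without flagged patients. State that improvement will be attributed to sodium correction only if its direction and approximate size hold in the repeat.

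Injuries and seizures are flagged, not excluded, because they may result from the hyponatremia.

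The cost is one line on the case report form, a little extra analysis and lower precision in the repeat. If 10% are flagged, 45 of 50 pairs remain and the standard error rises by √(50/45) = 1.05, about 5%; if 20%, 40 remain and it rises by √(50/40) = 1.12, about 12%. The repeat should therefore be judged on size and direction, not on whether p stays at or below 0.05. The change does not remove practice effects or regression to the mean, which any uncontrolled comparison of two visits carries.

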#### 3.2 Recruitment, screening and informed consent procedure

If a serum sodium of 125 mmol/L is detected in a blood sample sent from the Department of Emergency Medicine or General Internal Medicine, the Center for Laboratory Medicine will notify the study team (Drs. [name] and [name]) responsible for patient enrollment using a dedicated pager. Then, a member of the study team will approach potential participants, inform them about the study goals and procedures, obtain informed consent, and enroll them into the study. Patients enrolled in the Department of Emergency Medicine needing hospitalization will primarily be hospitalized in the Department of General Internal Medicine, unless hospitalization at specialist ward is indicated.

#### 3.3 Study procedures

Upon recruitment the following data will be collected:

##### a.) Clinical data

Of all patients included in the study, we will collect data on age, sex, comorbidities, and current medications taken by the patients.

##### b.) Serum sodium measurements

Measurements of serum sodium will be performed through the Center for Laboratory Medicine of the General Hospital Solothurn. Sodium determination will be performed by use of ion-selective electrode using the ICT (Na+, K+, Cl) Sample Diluent Kit, Abbott Laboratories, Chicago, IL, USA. Additionally, serum osmolality, potassium, magnesium, calcium, creatinine, albumin and hemoglobin as well as urine osmolality, sodium, potassium, creatinine and urea will be measured. All of these parameters are standard measurements in case of a severe electrolyte disorder and are part of clinical practice in the care for patients with electrolyte disorders. All laboratory parameters will be measured at baseline and after correction of serum sodium. In order to avoid multiple blood drawings for the patient the parameters mentioned above will be reordered from blood already taken for serum sodium determination.

##### c.) Physical and cognitive measurements

Afterwards muscle strength, Tinetti score and MOCA score will be measured. Upon correction of hyponatremia these measurements will be repeated. The study is then completed for the individual participant.

See also Appendix 1.

### 3.4 Withdrawal and discontinuation

Patients are excluded from the project in case of withdrawal of informed consent. Endpoint-specific datasets will be included if complete (see Section 4.2.). Additional patients will be enrolled to compensate for drop-outs. Since the blood samples used are part of clinical routine no further steps are taken, the blood samples will be handled according to usual clinical routine.

## 4 STATISTICS AND METHODOLOGY

### 4.1. Statistical analysis plan

Data will be presented as means and standard deviation or medians and interquartile range as appropriate. Wilcoxon signed ranked tests will be used to compare results on muscle strength, Tinetti score and MOCA scores, since those are not normally distributed and samples will be dependent since every patient serves as his own control. A p-value of  $\leq 0.05$  will be considered statistically significant. Statistics will be calculated using IBM SPSS Statistics 25, IBM, Armonk, New York, USA.

Based on general Patient count and prevalence of Hyponatremia, the enrollment of the sample size of 50 patients seems realistic in a 12-month period, starting on 01 June 2019.

